Study protocol

Project title: Hysteroscopic evaluation of Fallopian tubal patency compared to laparoscopic chromopertubation: a prospective, randomized study on the "flow" and "Parryscope" techniques

Brief title: Hysteroscopic evaluation of Fallopian tubal patency

Participants:

Investigator:

Assoc.[name].Doz. [name]

Participating Doctors:

[name]

Assoc. [name]. Doz. [name] a.o.Univ. [name]. [name]

Participating Clinics:

Medical University of Vienna, Department of Obstetrics

and Gynecology, Clinical Division of Gynecologic

Endocrinology and Reproductive Medicine

[name]

[name]

[contact]

[contact]

Introduction and scientific background:

Hysteroscopy is an important tool in the evaluation of sterility. [1-5] It allows direct visualization of the uterine cavity and enables the diagnosis of numerous pathologies, including endometrial polyps, intracavitary myomas and also more rare diseases associated with sterility and infertility, such as Asherman-syndrome and anomalies of the uterus itself. Hysteroscopy shows high reliability and is considered the gold standard for intrauterine evaluation [1-6].

When performing hysteroscopy, experts often assess the patency of the tubes via the visibility of flow of the hysteroscopic fluid going through the ostia of the tubes. In the recently published study "Assessment of tubal patency: A prospective comparison of diagnostic hysteroscopy and laparoscopic chromopertubation" it was demonstrated that visualizing contrasting substances disperse through the ostia is a significant and meaningful metric for tubal patency (sensitivity 85.2, 95% CI: 76.1-91.9; specificity: 66.1, 95% CI: 52.2-78.2). This confirmed the value of this approach, consistent with our previous retrospective study on the same topic [7]. Nevertheless, it is important to mention that the prospective study showed both a lower specificity (66.1% vs. 77.6%) and a lower positive predictive value (79.8% vs. 91.3%).

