Pre- and posthysteroscopic vaginal sonography for the evaluation of the hysteroscopic fluid in the pouch of Douglas [9,10], selective hysteroscopic pertubation of the tubes [11] and the visibility of air bubbles traversing through the Fallopian tube ostia after an air infusion into the uterine cavity [10,12] have been reported to be reliable methods for hysteroscopic tubal patency assessment. Particularly the last one, also called the "Parryscope technique", named after its inventor, seems to be highly reliable, easy to conduct and clinically relevant [8,10,12]. The "Parryscope technique" reaches a sensitivity of min. 98.3% and a specificity of 83.7% [9] and, thus, seems to perform even better than the technique evaluating the "tubal flow".

Assessing tubal patency during hysteroscopy is highly relevant, particularly when it allows for a low cost, fast, gentle, and accurate way of gathering information that may guide clinical care. Therefore, it is important to know which of the above-mentioned techniques is the best. This prospective randomized study aims to compare the hysteroscopic assessment of the tubes via "tubal flow" [7] and the "Parryscope technique" [10,12]. At our department, the Clinical Division of Gynecological Endocrinology and Reproductive Medicine of the Medical University of Vienna, a diagnostic hysteroscopy is usually performed directly before every infertility-related laparoscopy. These operations are always performed by an expert in the field of reproductive surgery, which should guarantee a good clinical quality of our data set.

Study aims:

The primary aim of this study is to evaluate the relalibility of (1.) the hysteroscopic visualization of a "tubal flow" and (2.) the "Parryscope technique" as compared to the gold standard, namely laparoscopic chromopertubation.

Study hypothesis:

Null hypothesis: The hysteroscopically visualizable "tubal flow" and the "Parryscope technique" are similarly reliable in the evaluation of tubal patency.

Alternative hypothesis: The hysteroscopically visualizable "tubal flow" shows a lower sensitivity and specificity than the "Parryscope technique" for the evaluation of tubal patency.

Study design:

Prospective, randomized study.

Participants:

Inclusion criteria:

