- The patient is subfertile, defined as being unable to become pregnant within a year despite unprotected sexual intercourse. It is also within the standard of care to be presumed subfertile if one has tried for six months and has known risk factors that would hinder conception, including but not limited to anovulation and endometriosis.
- A concurrent diagnostic hysteroscopy and laparoscopy with chromopertubation are performed at the Clinical Division of Gynecological Endocrinology and Reproductive Medicine at the Medical University of Vienna.
- The patient has given her written informed consent after detailed information on the study by medical professionals at the Department of Obstetrics and Gynecology of the Medical University of Vienna.
- The patient is ≥18 and ≤45 years old.

Exclusion criteria:

- The patient had a tubectomy on one or both sides.
- There is no "informed consent".
- The patients has active vaginal infection or other conditions that would preclude hysteroscopy.

Primary Outcome Parameters:

Hysteroscopic evaluation of tubal patency (either by a positive "tubal flow" or a visible flow of air bubbles in the "Parryscope technique") and the result of the laparoscopic chromopertubation (tubal patency existing or not existing).

Secondary Outcome Parameters:

For the descriptive analysis, several hysteroscopically visualizable additional parameters will be evaluated: (i) existence of any hysteroscopic abnormalities (including endometrial polyps, myomas, adhesions, anomalies or cervical stenosis). (ii) characteristics of the tubal "flow" – clearly visualizable or questionable, visualization of air bubbles and/or floating structures in the cavity. (iii) clarity of the hysteroscopic view (clear versus hazy).

Recruitment:

Women will be invited to participate by medical professionals at the Department of Obstetrics and Gynecology of the Medical University of Vienna using the above-mentioned criteria in the course of their admission to the ward one day before surgery. Potential participants are informed about the procedure, clinical relevance and the balance of risk and benefits incurred through study participation. Patients willing to participate will express this through written affirmation (a "consent form").

Parameters obtained:

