The following parameters will be collected and included in the database. They do not require additional effort on behalf of the patients. All data will be obtained using the study-specific case report form and will be entered into a SPSS database in a semi-anonymized manner.

- Patient's age
- Body mass index
- Primary/secondary subfertility
- Obstetrical history (gravidity, parity)
- History of risk factors relating to tubal disease (chlamydia infection, endometriosis, etc.)
- Detailed information about the indication for surgery
- Main outcome parameter 1: Hysteroscopic findings: tubal patency assumed or not assumed in right/left tubal ostium (information provided separately for each side)
- Additional findings: any hysteroscopic abnormalities (including endometrium polyps, myomas, adhesions, anomalies or cervical stenosis). In the "tubal flow" group an additional finding would also be the presence of air bubbles. Moreover, the clarity of the hysteroscopic view will be evaluated (clear versus hazy).
- Duration of the hysteroscopic evaluation of tubal patency (in minutes).
- Additional interventions: Curettage and operative hysteroscopy.
- Uterine length.
- *Main outcome parameter 2*: Laparoscopic findings: tubal patency as assessed by chromopertubation (information provided separately for each side)
- Amount of blue dye used in chromopertubation
- Performance of any additional laparoscopic interventions during the operation
- A subjective assessment of pressure used in demonstrating patency with chromopertubation (low vs high, which affects accuracy and prognosis)

The additional data acquisition will be conducted to give an exact characterization of the patient population to allow a comparison with the published literature.

Techniques of hysteroscopic evaluation of tubal patency:

"Tubal flow"-group: a positive "flow" is defined as the observation of saline directly traversing the ostia, endometrial structures floating toward the ostia, or air bubbles traversing the ostia.

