"Parryscope"-group: A small amount of air is introduced into the iv tubing by inverting the drip chamber to create air bubbles. When air enters the uterine cavity, a single large air bubble or stream of air bubbles traversing the ostia is considered indicative of tubal patency. At least 10 seconds of intracavitary evaluation is typically performed before air bubble entry to allow pressure equilibration if a hydrosalpinx is present [10]. At least 30 seconds of observation per ostia is performed if patency is not observed.

Additional considerations:

- 1. Since in the "flow"-group air bubbles might develop spontaneously and, thus, should be assessed, conducting the "Parryscope"-technique is only possible after the evaluation of the tubal flow
- 2. Reactive tubal spasms could occur especially during a prolonged hysteroscopy.
- 3. This is why in one particular patient only one technique should be performed.

Sample size calculation:

The calculation is based upon the following considerations:

- Direct comparison of the two groups is not possible. Hence, separate evaluation of the two
 methods will be performed. Evaluating both methods in one particular patient in the course
 of a single intervention is impossible without a mutual interference (see: "Additional
 considerations" above).
- 2. The "flow effect" is considered the less reliable method and thus, the sample size was aligned to this method. An odds ratio of approximately 10, an alpha of 5%, a power of 80%, a general disease likelihood of 39% and a sensitivity of 66% for occluded tubes result in a total amount of 59 tubes and, accordingly, 30 patients.
- 3. Thus, the group for the "Parryscope"-technique should also contain 59 tubes (= 30 patients).
- 4. The randomization of the total 60 patients is performed as block randomization in 4 blocks via the software "R".

Statistical analysis:

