Numerical data (age, body mass index) will be reported as mean and standard deviations, nominal variables (primary/secondary sterility, indication for the reproductive medical intervention, visibility of the "flow" in the left and right tubal ostium, pathologies in the uterine cavity in the hysteroscopy, patency of the tubes via chromopertubation, information about further laparoscopic interventions during the operation) as number and frequency. The McNemar Test will be used for the calculation of the reliability of the hysteroscopic assessment of the tubes. The sensitivity, specificity, positive and negative predictive values will be provided including the according 95% confidence intervals (95% CI) for both study groups (evaluated technique versus gold standard laparoscopic chromopertubation). The according odds ratio is over 10 will be evaluated by the use of a binary logistic regression model. Statistical analyses were performed with the software "R". Differences were considered significant if p<0.05.

Data quality evaluation:

Extreme values will be double-checked. In addition, random checks by two independent investigators will be conducted to ensure the accuracy of our data.

Risk-benefit-analysis:

In this prospective study, no further data acquisitions, follow-up examinations or surveys will be necessary. Except from the above-mentioned additional findings during the interventions, the only additional data to be collected would already be inherently obtained as part of procreative evaluation. Accordingly, if patients would be undergoing the described interventions (hysteroscopy, laparoscopy) independent of their choice to participate, this should not shift cost or risk for them. Additionally, since the study evaluations are minimal risk (visual observation of natural intracavitary flow patterns and deliberate addition of 0.5 mL of air in to saline during hysteroscopy (where greater amounts routinely enter the uterus accidentally through how lines are primed), safety should remain high. The analysis and publication of the data will be done with patient deidentification.

Agreement on the access of the principle investigator:

The principle investigator will have access to all study documents and statistics at all times.

References:

- 1. CHOLKERI-SINGH, A. & SASAKI, K. J. 2015. Hysteroscopy for infertile women: a review. J Minim Invasive Gynecol, 22, 353-62.

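### Both of a woman's tubes are counted and analysed as independent; if they are positively correlated, the planned intervals tend to be too narrow and the p-values too small

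*Combined protocol and SAP*

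**What the plan says.** - **Size.** Point 2 of the sample size calculation works in tubes and converts to patients by halving: "a sensitivity of 66% for occluded tubes result in a total amount of 59 tubes and, accordingly, 30 patients". Point 3 carries the same numbers over to the Parryscope arm. Randomisation is by patient.
- **Two tubes per woman.** One exclusion criterion reads "The patient had a tubectomy on one or both sides".
- **Data by side.** Under Parameters obtained, the hysteroscopic result is "tubal patency assumed or not assumed in right/left tubal ostium (information provided separately for each side"), and chromopertubation is recorded by side as well.
- **Analysis.** "The McNemar Test will be used for the calculation of the reliability of the hysteroscopic assessment of the tubes". Sensitivity, specificity and both predictive values get 95% intervals in each arm, and the odds ratio "will be evaluated by the use of a binary logistic regression model".

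The protocol nowhere mentions correlation within a woman, a design effect, GEE, a random effect, robust variance or a per-woman analysis. The tube as unit of analysis is implied by the sample size and the McNemar sentence; it is not stated outright.

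**The concern.** Two tubes from one woman are unlikely to be independent. The protocol itself lists factors that act on both sides at once: history of tubal risk factors, a clear or hazy view, and "A subjective assessment of pressure used in demonstrating patency with chromopertubation (low vs high, which affects accuracy and prognosis"). If such factors make occlusion, or correct calls, agree within a woman, 60 tubes carry less information than 60 independent tubes. The planned formulas would not see this.

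The sample size section says the two arms cannot be compared directly and will be evaluated separately. The per-arm accuracy estimates, their intervals and the McNemar and odds-ratio results are therefore the main findings of the trial. Overstated precision would fall on those findings.

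**Working it through.** **1. The plan's own figure.** 59 / 2 = 29.5, rounded up to 30 women. The design effect used is exactly 1. The protocol names no formula for the 59. The closest match found is a logistic-regression sample size with a binary covariate, independent tubes, two-sided alpha 5%, power 80%, covariate prevalence 0.39 and baseline proportion 0.66. It gives 61 tubes at an odds ratio of 10 and 59 at 11. A more natural diagnostic reading (66% of occluded against 16.3% of patent tubes called occluded, odds ratio 10) gives 31 tubes, or 39 with continuity correction. None of these readings contains a clustering term.

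**2. Where the inputs seem to come from (inference from the numbers).** The Introduction quotes "sensitivity 85.2, 95% CI: 76.1-91.9; specificity: 66.1, 95% CI: 52.2-78.2" for an earlier study. A search over all x/n with n from 10 to 400, using exact, Wilson and Wald intervals, reproduces these only as 75/88 and 37/56 with exact binomial intervals. From those counts:
- occluded: 56/144 = 38.9%
- occlusions detected: 37/56 = 66.1%
- predictive value of a patent call: 75/(75 + 19) = 79.8%, as quoted in the Introduction
- odds ratio: (75 × 37)/(13 × 19) = 11.2

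These match the sample size inputs of 39%, 66% and about 10. If the counts are tubes, as they appear to be, the planning figures carry no clustering allowance either. The point does not depend on this step.

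**3. Effective numbers.** An arm of 60 tubes has 0.39 × 60 = 23.4 occluded and 36.6 patent tubes. An occluded tube has an occluded partner with probability 0.39 + 0.61 × ICC(disease), and only such pairs are correlated in the sensitivity estimate. Hence:
- occluded tubes: design effect = 1 + ICC(calls) × [0.39 + 0.61 × ICC(disease)]
- patent tubes: design effect = 1 + ICC(calls) × [0.61 + 0.39 × ICC(disease)]

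With both ICCs at 0.5, the first is 1 + 0.5 × 0.695 = 1.3475, and 23.4 / 1.3475 = 17.4. The approximate half-width for 66% goes from 1.96 × √(0.66 × 0.34 / 23.4) = 19.2 points to 1.96 × √(0.66 × 0.34 / 17.4) = 22.3 points.

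| ICC (assumed) | 0.2 | 0.33 | 0.5 | 0.6 |
|---|---|---|---|---|
| 23.4 occluded tubes count as | 21.2 | 19.6 | 17.4 | 16.1 |
| 36.6 patent tubes count as | 32.2 | 29.4 | 26.1 | 24.3 |

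The simple 60/(1 + ICC) is only a lower bound (40 at ICC 0.5).

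**4. Operating characteristics.** 20,000 simulated arms per scenario: 30 women × 2 tubes, 39% occluded, 66% of occluded and 85.2% of patent tubes called correctly, correlation generated through latent normals. The ICC is on the scale of the binary outcomes and is the same for disease and correct calls. The McNemar null sets specificity for occlusion at 78.3%, so that 0.39 × 0.34 = 0.61 × 0.217. The odds-ratio null makes test and reference independent of each other, but each clustered. Monte Carlo error is about 0.2 to 0.4 points.

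| ICC (assumed) | 0 | 0.2 | 0.33 | 0.5 | 0.6 |
|---|---|---|---|---|---|
| Coverage, 66% sensitivity, Wilson | 95.4% | 94.0% | 93.0% | 91.3% | 89.8% |
| Same, exact | 97.2% | 95.9% | 95.3% | 94.0% | 92.5% |
| Coverage, predictive value of a patent call, Wilson | 95.3% | 93.2% | 91.5% | 89.8% | 88.5% |
| Same, exact | 97.2% | 95.5% | 94.4% | 92.9% | 91.8% |
| McNemar alpha, uncorrected | 5.0% | 5.6% | 7.0% | 8.6% | 9.9% |
| McNemar alpha, continuity-corrected | 2.6% | 2.9% | 3.9% | 5.3% | 6.1% |
| Logistic Wald test alpha, odds ratio 1 | 4.5% | 5.2% | 6.2% | 7.6% | 8.8% |
| Coverage, odds ratio 11.2 | 96.2% | 94.4% | 93.3% | 91.9% | 90.8% |

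**5. One source of correlation at a time (Wilson).** If only disease correlates (ICC 0.33 / 0.5 / 0.6), sensitivity and specificity keep 95.2–95.3% coverage, but the predictive value of a patent call covers 93.5 / 92.7 / 92.2%. If only correct calls correlate (0.33 / 0.5), sensitivity covers 93.8 / 93.1% and specificity 93.3 / 92.1%.

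**6. Power.** Against an odds ratio of 1, power is 96–99% unadjusted and 87–98% with cluster-robust variance over the same ICC range.

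**The case against.** The strongest reply is that the harm is conditional and often modest.

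- The documents give no ICC, and values of 0.5 to 0.6 are assumptions.
- Exact intervals and the continuity-corrected McNemar test start out conservative, and correlation uses up that margin first. Exact coverage for sensitivity is still 95.3% at ICC 0.33, and the corrected McNemar test is at 3.9%. If the team uses exact intervals, as the earlier study's figures suggest, the exact rows are the relevant ones.
- The ICC scale matters. Read as a latent correlation, 0.5 gives about 92.9% coverage for Wilson and 95.3% for exact.
- The logistic test is inflated only if disease and test results both cluster; with one alone it stays near 4%. The plan also speaks of an odds ratio over 10, so error at an odds ratio of 1 has little practical weight.
- The sample size itself is not shown to fail.

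All of this stands as a limit on size. It does not remove the gap. The plan names neither an interval type nor a McNemar version, so its validity would rest on an unstated choice. The predictive value of a patent call falls below 95% even with exact intervals at ICC 0.33 (94.4%). The interval for an odds ratio of 11.2, near the planned effect, also under-covers. The remedy below is one sound choice; another standard cluster-adjusted method would also do.

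**Conclusion.** The point holds and should be fixed. The plan uses a design effect of 1 and analyses paired tubes as if they were independent. That the allowance is missing is certain from the text. How much it matters depends on an ICC that the documents do not give:

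- **ICC 0.2 or below:** small.
- **ICC 0.33 to 0.6:** nominal 95% intervals for sensitivity cover 93.0% down to 89.8% (Wilson) or 95.3% down to 92.5% (exact). A nominal 5% McNemar test runs at 7.0% to 9.9% uncorrected, or 3.9% to 6.1% corrected.

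These figures assume equal ICCs for disease and correct calls and the protocol's own accuracy inputs. No loss of power below 80% and no need for more patients is claimed.

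**What to change.** In the Statistical analysis section, name the tube as unit of analysis and the patient as cluster, and specify:

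1. **Sensitivity, specificity and predictive values:** a Wilson interval with n divided by the estimated design effect (cluster-robust over binomial variance, not below 1) and a t quantile on 29 degrees of freedom. Simulated coverage is 94.2–96.9% over ICC 0 to 0.6. A patient-level bootstrap is an alternative, but it collapses to zero width when the estimate is 100%.
2. **McNemar:** a clustered version on differences summed within patient (simulated alpha 4.5–4.9%).
3. **Odds ratio:** GEE logistic regression with independence working correlation, small-sample robust variance and t on 28 degrees of freedom (coverage about 97%, alpha 3.3–4.0%). State in advance that with an empty cell the odds ratio is reported as not estimable and the intervals in item 1 are used.

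In the sample size section, give the size as 30 patients (60 paired tubes) per arm, say that 59 tubes assumes independence, and show the effective numbers over a stated ICC range with the formulas above.

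**Cost.** Some wording and a few lines of R; both sides are already recorded. The sensitivity interval is 7% (ICC 0) to 21% (ICC 0.6) wider than plain Wilson, and that for the predictive value of a patent call up to 28% wider. There is slight over-coverage if the ICC is near 0. GEE with 30 clusters is fragile in sparse tables. The Introduction says the Parryscope technique "reaches a sensitivity of min. 98.3% and a specificity of 83.7"%; reading these as figures for patency, with 39% occlusion, a cell is empty in about 55–62% of simulated trials. Ordinary logistic regression fails there too.

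### The McNemar test is named as the measure of reliability, but within an arm it tests only whether the two kinds of error are equally frequent

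*Combined protocol and SAP*

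**What the plan says.** The Study aims section opens with "The primary aim of this study is to evaluate the relalibility of" each technique, with laparoscopic chromopertubation as the gold standard. The Statistical analysis section then gives that same word to one test: "The McNemar Test will be used for the calculation of the reliability of the hysteroscopic assessment of the tubes".

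Two other statements decide what the test can be applied to. Under Additional considerations: "This is why in one particular patient only one technique should be performed". Under Sample size calculation: "Direct comparison of the two groups is not possible".

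The sentence after the McNemar sentence plans sensitivity, specificity and both predictive values with 95% confidence intervals for each group against chromopertubation. A logistic-regression odds ratio follows, and then a general significance level of p<0.05. Nothing says how the McNemar p-value is to be read. The alternative hypothesis is worded in accuracy terms (flow "shows a lower sensitivity and specificity than the" Parryscope technique), but it concerns the contrast between techniques, not each technique against the gold standard.

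**The concern.** With one technique per patient and no direct comparison of the groups, the only pairs available to a McNemar test are the hysteroscopic call and the chromopertubation result for the same tube. The test then uses only the two discordant cells and asks whether they are equal. Correctly classified tubes do not enter it, and neither does the total number of errors.

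A non-significant result means that no net over- or under-calling of patency was detected. A significant result means that there was some, which is one component of reliability, but it does not mean that overall accuracy is low. Because the primary aim is worded as reliability and the McNemar sentence uses that word, p>0.05 could be reported as showing that a technique is reliable. In the same way, p<0.05 could be held against a technique that agrees well with the gold standard.

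**Working it through.** **Notation.** Patent is the positive result. For each arm, a = patent tubes called patent, b = patent called occluded, c = occluded called patent, d = occluded called occluded, n = a+b+c+d.

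- Sensitivity = a/(a+b); specificity = d/(c+d), both with exact (Clopper-Pearson) 95% intervals.
- Exact McNemar p = 2 × P(X ≤ min(b,c)), X ~ Binomial(b+c, ½), capped at 1.
- Kappa = (Po − Pe)/(1 − Pe), with Po = (a+d)/n and Pe = [(a+b)(a+c) + (c+d)(b+d)]/n².

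The p-value depends on b and c alone.

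**Step 1: recover the earlier flow data.** The Introduction gives "sensitivity 85.2, 95% CI: 76.1-91.9; specificity: 66.1, 95% CI: 52.2-78.2". A search over all fractions k/n with n up to 299 and exact intervals finds one match for each: 75/88 and 37/56. The counts are derived, not printed, but they agree with three other figures in the protocol:

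- PPV 75/(75+19) = 75/94 = 79.8%, the first figure in "a lower positive predictive value (79.8% vs. 91.3"%);
- occlusion 56/144 = 38.9% and detection of occluded tubes 37/56 = 66.1%, matching "a general disease likelihood of 39% and a sensitivity of 66% for occluded tubes" in the sample size section.

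So a = 75, b = 13, c = 19, d = 37, n = 144.

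**Step 2: apply the test to those data.** With 13 and 19 discordant tubes, exact p = 0.377 (uncorrected chi-square (19−13)²/32 = 1.125, p = 0.289). Misclassified: 32/144 = 22.2%. Po = 112/144 = 0.778; Pe = (88×94 + 56×50)/144² = 0.534; kappa = 0.523. The non-significant p-value gives no hint that more than one tube in five is misread.

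**Step 3: two illustrations at about the planned size.** 60 tubes at 39% occlusion give 37 patent and 23 occluded. These tables are illustrations, not expected results.

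| | b = 14, c = 14 | b = 0, c = 6 |
|---|---|---|
| Correct | 32/60 = 53% | 54/60 = 90% |
| Sensitivity | 23/37 = 62.2% (44.8–77.5) | 37/37 = 100% (90.5–100) |
| Specificity | 9/23 = 39.1% (19.7–61.5) | 17/23 = 73.9% (51.6–89.8) |
| Pe | (37×37 + 23×23)/3600 = 0.527 | (37×43 + 23×17)/3600 = 0.551 |
| Kappa | 0.013 | 0.778 |
| Odds ratio ad/(bc) | 23×9/(14×14) = 1.06 | infinite (b = 0) |
| Exact McNemar p | 1.00 | 2×(½)⁶ = 0.031 |

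The test passes the chance-level technique and flags the far better one. When all errors run one way, five are not enough (2×(½)⁵ = 0.0625) and six are.

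**Step 4: behaviour at the plan's own inputs.** Take 59 tubes, 39% occluded: 23.0 occluded, 36.0 patent.

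- Flow: 23.0 × 0.34 = 7.8 occluded tubes called patent. Patent tubes called occluded: 36.0 × 0.148 = 5.3, using the 85.2% in the Introduction, or 36.0 × 0.163 = 5.9, using the 83.7% that an odds ratio of 10 implies alongside 66%. Exact McNemar power is about 3–6%.
- Parryscope, at the cited 98.3% and 83.7%: 23.0 × 0.163 = 3.8 against 36.0 × 0.017 = 0.6. Power is about 9–11%.

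The ranges cover the assumed rates and whether the number of occluded tubes is fixed or random. A non-significant result is close to certain for flow, and the technique expected to be more accurate is the likelier one to give p<0.05.

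**The case against.** The strongest reply is that nothing is missing. The sentence after the McNemar sentence plans sensitivity, specificity and predictive values with confidence intervals against chromopertubation, which is the primary aim. The planned odds ratio also separates the two illustrations (1.06 against infinite), and the sample size targets an odds ratio of about 10, not a McNemar result. The plan never says that p>0.05 means reliable. The 14-and-14 table is also well below the accuracy that the protocol cites for either technique.

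Most of this stands, and it limits the harm. Accuracy will be estimated whatever McNemar shows, and the illustration shows what the test permits, not what is likely. It does not rescue the sentence, which attaches the key word of the primary aim to a statistic that does not measure it. The flow data in step 2 are not an extreme case, and they show the same gap between p-value and accuracy.

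A further objection is that naming sensitivity and specificity as the measure exposes their imprecision: with 23 occluded tubes, the specificity interval in the second illustration runs from 52% to 90%. That is true, but the intervals are already planned and would be equally wide under any label.

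**Conclusion.** The concern holds. The stated analysis does not measure what the plan says it measures: within an arm, McNemar detects a directional imbalance of errors, not accuracy or agreement. The p-value can be 1.00 at kappa 0.01 and 0.031 at kappa 0.78. On the recovered flow data it is 0.38 with 22% of tubes misclassified.

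The fault is one of labelling and should be fixed. It changes which statistic answers the primary aim, but no accuracy analysis is absent and no decision rule or sample size depends on the test.

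The figures rest on three assumptions: the flow counts are back-calculated, the 60-tube tables are illustrative, and tubes are treated as independent, as an ordinary McNemar test does, although most patients contribute two. The last affects the exact p-values and intervals, not the argument.

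**What to change.** Rewrite the McNemar sentence in the Statistical analysis section. State that the reliability of each technique against chromopertubation is judged by its sensitivity and specificity with 95% confidence intervals, as already planned. Then either delete McNemar, or keep it as a descriptive check for systematic over- or under-calling of patency and state that no conclusion about reliability is drawn from its p-value.

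The odds-ratio analysis stays as it is. The cost is one sentence, with no change to data collection, sample size or randomisation.

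### At the protocol's own figures the planned logistic regression gives an infinite odds ratio in about 55% of Parryscope-arm data sets, and no method is named for that case

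*Combined protocol and SAP*

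**What the plan says.** The Statistical analysis section plans sensitivity, specificity and predictive values with 95% confidence intervals for both groups, a McNemar test, and an odds ratio: "The according odds ratio is over 10 will be evaluated by the use of a binary logistic regression model". Its decision rule is "Differences were considered significant if p<0.05". The software is R. No exact, penalised or profile-likelihood method is named, and empty cells are not mentioned.

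The Sample size calculation treats the techniques separately ("Direct comparison of the two groups is not possible"). It sizes the flow arm from "An odds ratio of approximately 10, an alpha of 5%, a power of 80"% together with "a general disease likelihood of 39% and a sensitivity of 66% for occluded tubes", and carries the result over to the other arm, which "should also contain 59 tubes (= 30 patients"). The expected accuracy of the Parryscope technique is in the Introduction: "The 'Parryscope technique' reaches a sensitivity of min. 98.3% and a specificity of 83.7"%.

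**The concern.** Logistic regression on a 2x2 table has a finite maximum-likelihood odds ratio only if all four cells are occupied. A technique that rarely misreads a patent tube, tested on a few dozen patent tubes, will often leave the patent-but-called-blocked cell at zero. The software then stops at an arbitrary large coefficient with a huge standard error, and the Wald p-value in the default summary is close to 1.

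This affects the arm expected to perform better and almost never the other. Read literally against the p<0.05 rule, near-perfect agreement with chromopertubation would be reported as no association, beside a clearly significant odds ratio for the flow technique. If the remedy is chosen only after the empty cell is seen, it becomes a post hoc decision.

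**Working it through.** **Which tubes the 98.3% applies to.** The Introduction gives the prior prospective flow study as sensitivity 85.2% and specificity 66.1%, with "a lower positive predictive value (79.8% vs. 91.3"%). The sample-size section's 66% for occluded tubes matches that specificity, so sensitivity means detecting patency. Check with 39% occlusion:

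PPV = 0.852 × 0.61 / (0.852 × 0.61 + 0.339 × 0.39) = 0.797, against the stated 79.8%.

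So 98.3% applies to the patent tubes: 0.61 × 59 ≈ 36.

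**The plan's 59 tubes.** This figure is taken as given. It could not be reproduced from the stated inputs: comparing proportions at an odds ratio of 10, 66%, 39%, 5% and 80% power needs 24 to 39 tubes, depending on sidedness and continuity correction. The present point does not depend on how 59 was reached.

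**Probability of an empty cell, Parryscope arm.** Tubes are treated as independent, with occluded tubes ~ Binomial(n, 0.39).

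- Expected patent tubes called blocked: 36 × 0.017 = 0.61.
- No patent tube called blocked: (1 − 0.61 × 0.017)^n = 0.541 for n = 59, 0.535 for n = 60.
- No occluded tube called patent: (1 − 0.39 × 0.163)^n = 0.021 and 0.019.
- Any empty cell, by inclusion-exclusion over all four cells: 0.551 (n = 59), 0.544 (n = 60).
- With margins fixed at 36 patent and 23 occluded tubes: 0.547.

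| Sensitivity | P(empty cell), n = 59 | n = 60 |
|---|---|---|
| 95% | 0.18 | 0.17 |
| 97% | 0.35 | 0.34 |
| 98.3% | 0.55 | 0.54 |
| 99% | 0.70 | 0.70 |

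At 98.3% sensitivity, occlusion between 25% and 50% gives 0.51 to 0.61. Assumed within-patient correlation of 0.3 to 0.5 in tubal status and reading error gives 0.59 to 0.62. The flow arm (85.2%, 66.1%) gives 0.004.

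**What the model returns.** Example with 60 tubes: 37/37 patent and 19/23 occluded tubes read correctly.

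| Method | Result |
|---|---|
| R glm, Wald | slope 21.8, SE 2467, p = 0.993, interval 0 to infinity |
| R confint() on the same fit | no usable lower limit (−115 on the log scale, with warnings) |
| Likelihood-ratio test, same fit | p = 2.4×10^-13 |
| Fisher exact | p = 4×10^-12, exact lower limit 26.5 |
| Firth, profile interval | OR = 37.5 × 19.5 / (0.5 × 4.5) = 325, 95% CI 34 to 44,000, p = 2×10^-12 |

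**How often the 95% interval excludes an odds ratio of 1** (59 tubes, all tables enumerated, an empty cell counted as no answer for Wald).

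| Arm | Wald | Firth profile |
|---|---|---|
| Parryscope, 98.3% | 0.449 | 1.000 |
| Parryscope, 97% | 0.649 | 1.000 |
| Parryscope, 95% | 0.821 | 1.000 |
| Flow | 0.981 | 0.985 |

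In the Parryscope rows the Wald shortfall is simply the empty-cell probability (1 − 0.551 = 0.449), not a separate loss of power.

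**Operating characteristics of Firth, n = 59, independent tubes.** Coverage is 96.1% (Parryscope) and 95.2% (flow). Rejection at a true odds ratio of 1 is at most 4.8% over five settings. The median estimate is 212 against a true (0.983/0.017) × (0.837/0.163) = 297 for Parryscope, and 10.8 against a true 11.2 for flow.

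**The case against.** **The plan never says Wald.** It names a model, a software package and a threshold. The likelihood-ratio test of the same unpenalised fit gives p = 2.4×10^-13 in the example, so a usable p-value exists within the stated model. This stands for the p-value. The infinite point estimate and the lack of a usable default interval remain, and Wald is what R's standard summary prints.

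**The sentence concerns an odds ratio over 10, not one different from 1.** If that is judged on the point estimate, infinity gives the right answer. The plan does not say how it is judged, so this cannot be excluded. A reader would also see that an interval from 0 to infinity is a failed fit, next to an observed sensitivity of 100%.

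**The sentence is garbled and may concern only the flow arm**, since an odds ratio of about 10 appears elsewhere only for that method. It directly follows a sentence covering both groups, so the two-arm reading is the more likely one, but not certain.

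**The 55% rests on one cited sensitivity** and falls quickly below it. That is so, and the range is given above. The protocol presents 98.3% as a minimum, which points the other way.

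**Firth does not handle two tubes per patient.** Correct. In a simulation with assumed latent within-patient correlation of 0.5 or 0.8, its flow-arm coverage fell to about 92% or 88%. The coverage figures above hold for independent tubes only.

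**Conclusion.** The concern holds, as a minor one. At the protocol's own accuracy, occlusion and sample-size figures, the named method gives no finite odds ratio and no usable default interval in about 55% of Parryscope-arm data sets, against 0.4% in the flow arm. This rests on independent tubes, a sensitivity of 98.3% for patent tubes (0.18 to 0.70 over 95% to 99%), and the odds-ratio sentence applying to both arms. The damage is confined to the odds-ratio analysis, which is not among the stated aims or outcomes. Sensitivity, specificity, predictive values and the McNemar test are untouched.

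**What to change.** Add to the Statistical analysis section: *In each arm the odds ratio is estimated by Firth penalised logistic regression with a profile penalised-likelihood 95% CI and p-value; Wald intervals and p-values are not used.* An exact conditional odds ratio can serve as a check.

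The cost is one sentence and a standard R package, with no change to sample size or data collection. With independent tubes the flow arm loses nothing (0.985 against 0.981). The price is shrinkage of the estimate, larger in the Parryscope arm (212 against 297) than in the flow arm (10.8 against 11.2), and a very wide upper limit when a cell is empty (about 44,000 in the example).

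Two matters are left open. The change supplies no rule for judging an odds ratio over 10. Requiring the lower limit to exceed 10 should not be read into it, because the flow arm would meet that in only about 3% of trials (0.031). It also makes no allowance for the pairing of tubes within a patient, which needs its own provision.
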